The proposed study is to compare the pharmacokinetics and pharmacodynamics micro-doses (0.05 and 0.03 mg) of freshly reconstituted Lilly glucagon with Xeris glucagon in healthy volunteers with type 1 diabetes. The hyperinsulinemic-normoglycemic clamp protocol is the standard method to perform pharmacokinetic and pharmacodynamics studies on drugs that effect BG. The doses of glucagon chosen for this study are in the range of doses that are routinely given by the bi-hormonal bionic pancreas. They are expected to result in a modest but easily measureable decrease in the glucose infusion rate (GIR), and will be directly relevant to infusion in the context of a bi-hormonal bionic pancreas. The direct comparison of Lilly glucagon (which has been used in all of the bi-hormonal bionic pancreas studies to date) and Xeris glucagon will provide the

preliminary data required to obtain FDA evaluation of Xeris glucagon in future bionic pancreas studies.

II. Hypothesis and Specific Aims

We hypothesize that Xeris glucagon will be non-inferior to freshly reconstituted Lilly glucagon both in terms of pharmacokinetics (t_{max} , $t_{1/2max}$) and pharmacodynamics (AUC_{GIR}), and in terms of safety. The specific aims of this study are:

Aim 1. To compare the pharmacokinetics and pharmacodynamics of Lilly and Xeris glucagon after low-dose subcutaneous injection using the hyperinsulinemic-normoglycemic clamp technique in volunteers with type 1 diabetes.

Aim 2. To document any adverse events of the Xeris glucagon formulations after subcutaneous injection in volunteers with type 1 diabetes.

III. Subject Selection

III. a. Inclusion Criteria

- Age 21 to 80 years old with type 1 diabetes for at least one year.
- Diabetes managed using an insulin infusion pump using rapid-acting insulin such as insulin aspart (NovoLog), insulin lispro (Humalog), or insulin glulisine (Apidra) for at least one week prior to enrollment.

III. b. Exclusion Criteria

- Unable to provide informed consent.
- Unable to comply with study procedures.
- Current participation in another diabetes-related clinical trial that, in the judgment of the principle investigator, will compromise the results of the clamp study or the safety of the subject.
- Pregnancy (positive urine HCG), breast feeding, plan to become pregnant in the immediate future, or sexually active without use of contraception.
- End stage renal disease on dialysis (hemodialysis or peritoneal dialysis).

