During the hyperinsulinemic-normoglycemic clamp:

- Venous BG measurements
- Timing and size of glucagon doses
- Insulin infusion rate
- Glucose infusion rates
- Plasma insulin levels every 15-30 minutes during the hyperinsulinemic-normoglycemic clamp

- Plasma glucagon levels every 2-15 minutes during the hyperinsulinemic-normoglycemic clamp
- Any adverse events, including nausea, vomiting, pain, and any local reactions to glucagon injection

VI. b. Study Endpoints

Primary endpoint analysis:

- Glucagon t_{\max} for Xeris vs. Lilly (non-inferiority)

Secondary endpoint analyses:

- Area over the curve for glucose infusion rate in the hour following a subcutaneous glucagon dose (AOC_{GIR}) for Xeris vs. Lilly
- Maximal glucose infusion rate (GIR_{\max}) for Xeris vs. Lilly
- Glucagon $t_{\frac{1}{2}\max}$ for Xeris vs. Lilly
- Quantitation of adverse events related to glucagon injection for Xeris vs. Lilly:
 - Injection pain on a 10 cm standard VAS: 0 = no pain, 10 = worst imaginable pain
 - Injection site erythema or other local reaction, maximum diameter within 1 hour of injection
 - Maximal nausea within 1 hour of injection on a 10 cm VAS: no nausea = 0, vomiting = 10

We will calculate means, median, percentages, standard deviations, standard errors, inter-quartile ranges, and 95% confidence intervals in descriptive analyses. We will use paired t-test for comparison of means. We will use multivariate regression models with repeated measurements to compare means and percentages while adjusting for patient demographics characteristics such as age, gender, body mass index, and body surface area.

VI. c. Power Analysis

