Our previous clinical study found a mean $t_{\max} \pm SD$ for Lilly glucagon after subcutaneous injection of 50 mcg of 15.8 ± 3.52 min (Appendix C). A previous pre-clinical PK/PD study in diabetic swine found no significant difference in t_{\max} between Lilly and Xeris glucagon (Appendix B). This study is powered to achieve 90% power to determine non-inferiority of Xeris vs. Lilly glucagon t_{\max} using a one-sided t-test when the margin of equivalence is 2.52 minutes (15% of the t_{\max} for Lilly glucagon in humans) and the true difference between the means of Lilly and Xeris glucagon is assumed to be 0. Therefore, the null hypothesis is that the t_{\max} of Xeris glucagon is not worse than the t_{\max} of Lilly glucagon by more than 2.52 minutes. The assumed standard deviation for each glucagon is 3.52 based on the clinical data. We assume a correlation coefficient between Lilly and Xeris glucagon within the same subject to be 0.7 in this crossover design, resulting in an SD of 2.73 in the difference between the two. The significance level (alpha) of the test is

0.05. The sample size required to achieve the designated power is 12 clamp experiments, each including one injection of Lilly glucagon and one injection of Xeris glucagon.

VII. Risks and Discomforts

There is a potential risk of nausea or vomiting in volunteers due to the administration of exogenous glucagon. The experiments, however, involve small subcutaneous glucagon doses. The recommended dose of glucagon for treatment of severe hypoglycemia in an adult with diabetes is 1000 mcg, given as a single subcutaneous or intramuscular injection. In practice, a smaller dose of 500 mcg is sometimes used initially to reduce the risk of nausea and vomiting. The total dose to be administered in our study is 100 mcg.

There is a potential risk of hypoglycemia, since exogenous insulin will be administered. Given frequent BG monitoring (every two to five minutes), corresponding adjustment of a continuous dextrose infusion, and direct supervision by an NP or MD at all times, the risk of a hypoglycemic episode leading to significant harm to volunteers is expected to be very low. A small meal will be provided to subjects after completion of the study.

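### The pharmacokinetic non-inferiority claim rests on t_max and t½max, which describe rate of absorption; no plasma glucagon endpoint measures how much is absorbed

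*Combined protocol and SAP*

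**What the plan says.** The hypothesis in Section II is that "Xeris glucagon will be non-inferior to freshly reconstituted Lilly glucagon both in terms of pharmacokinetics" (t_max, t½max), and also in pharmacodynamics (AUC_GIR) and safety. Aim 1 is "To compare the pharmacokinetics and pharmacodynamics of Lilly and Xeris glucagon after low-dose subcutaneous injection".

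Section VI.b makes glucagon t_max the primary endpoint and labels it, alone, as a non-inferiority comparison. The secondary endpoints are t½max, GIR_max, adverse event measures and AOC_GIR, described as "Area over the curve for glucose infusion rate in the hour following a subcutaneous glucagon dose". For analysis the section states "We will use paired t-test for comparison of means" and mentions adjusted regression models. No plasma glucagon AUC, Cmax or relative bioavailability is listed.

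Section VI.c says "This study is powered to achieve 90% power to determine non-inferiority of Xeris vs. Lilly glucagon". The endpoint there is t_max, the test is one-sided, and the margin is 2.52 minutes. No other endpoint has a margin.

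The data for an exposure measure will exist. Section VI.a lists "Plasma glucagon levels every 2-15 minutes during the hyperinsulinemic-normoglycemic clamp", and Section V.d has plasma processed every two minutes for the hour after each injection.

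**The concern.** Pharmacokinetic comparability has two parts: how fast the drug arrives and how much arrives. The plan measures only the first. Section V.b describes a change of vehicle (mainly DMSO instead of aqueous) and a five-fold higher concentration (5 against 1 mg/ml), so the amount absorbed is an open question. Section I.d says that human pharmacokinetic data for Xeris glucagon are not yet available, and the swine results in Section I.b give times and a glucose response but no glucagon exposure figure.

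Section I.d intends the comparison as preliminary data for FDA evaluation of Xeris glucagon in bionic pancreas studies. A device that doses in micrograms depends on how much glucagon each microgram delivers as well as on its timing. A conclusion of non-inferior pharmacokinetics drawn from two times would be silent on that.

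**Working it through.** **1. The plan's own figure.** Inputs from Section VI.c: SD 3.52 minutes per formulation, correlation 0.7, margin 2.52 minutes, true difference 0, one-sided alpha 0.05, power 90%.

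- SD of the paired difference = √(2 × 3.52² × (1 − 0.7)) = 2.73, as stated.
- Normal approximation: n = (2.73 × (1.645 + 1.282) / 2.52)² = 10.05, rounded up to 11.
- Exact noncentral t: the smallest n reaching 90% is 12, with power 91.1%.

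The stated 12 experiments are reproduced. The calculation concerns t_max only.

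**2. What the two times can detect.** If absorption and elimination rates are unchanged, kinetics are linear and baseline is subtracted, then changing bioavailability from 1 to F multiplies the whole curve by F. The peak stays at the same time, and the curve crosses half its own peak at the same time.

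Illustration, with assumed rate constants that are not in the documents (ka = 0.09/min, ke = 0.045/min) and a dose D of 50 mcg:

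C(t) = F × D × ka/(ka − ke) × (e^(−ke·t) − e^(−ka·t))

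- t_max = ln(ka/ke)/(ka − ke) = ln 2/0.045 = 15.4 min, with no F in the formula.
- Cmax at F = 1: 50 × 2 × (0.50 − 0.25) = 25.0 (arbitrary units).

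| | F = 1 | F = 0.5 |
|---|---|---|
| t_max (min) | 15.4 | 15.4 |
| rising t½max (min) | 3.5 | 3.5 |
| Cmax | 25.0 | 12.5 |
| AUC0-60 | 967 | 483 |

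A second assumed set (ka = 0.08, ke = 0.045, read every 2 minutes) gives t_max 16 and t½max 3.8 minutes at every F tried (1, 0.6, 0.5, 0.3). The values depend on the constants; the invariance does not.

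So, under the Section VI.c assumptions, the chance of passing the t_max test at n = 12 is 91.1% at full bioavailability and 91.1% at half. A larger sample would not change this insensitivity.

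**3. What AOC_GIR would face.** Raw exposure ratio, Xeris/Lilly = relative bioavailability × Xeris dose / Lilly dose.

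| Relative bioavailability | 50 mcg Xeris, 30 mcg Lilly (Section V.d) | Equal doses |
|---|---|---|
| 1.0 | 50/30 = 1.67 | 1.00 |
| 0.6 | 30/30 = 1.00 | 0.60 |
| 0.5 | 25/30 = 0.83 | 0.50 |
| 0.3 | 15/30 = 0.50 | 0.30 |

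At the Section V.d doses, a halving of bioavailability is largely offset by the larger Xeris dose. The documents give no variability for AOC_GIR and no exposure-response relation, so the chance of detecting a ratio of 0.83 in 12 pairs cannot be computed.

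**4. The dose statements side by side.** Section V.d: 30 mcg Lilly and 50 mcg Xeris. Section V.e: two doses of 30-50 mcg, total 80 mcg. Section VII: total 100 mcg. Since 30 + 50 = 80, Section VII disagrees with the other two.

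**The case against.** The strongest reply is that the plan does contain a measure that depends on exposure. The hypothesis requires pharmacodynamic as well as pharmacokinetic non-inferiority, Section I.d chose doses expected to give a measurable fall in glucose infusion rate, and a loss of absorbed glucagon should reduce AOC_GIR. A reader might infer that the trial as a whole could declare Xeris non-inferior at half the exposure. The documents do not support that, because the pharmacokinetic result is only one leg of the hypothesis.

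What remains is that AOC_GIR is not a formal safeguard. It has no margin or decision rule, and a non-significant paired t-test in 12 pairs does not establish non-inferiority. GIR_max adds little: glucagon lowers the infusion rate, so a maximum does not capture its peak effect.

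A second reply is that the invariance is conditional. A new solvent could change rate and extent together, and loss at the injection site that competes with absorption would shift t_max. Section VI.b neither defines t½max nor specifies baseline subtraction, and endogenous glucagon could add noise to both times at low exposure. This stands: it would be too strong to say that the two times never respond to reduced absorption. The point is that they need not.

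A third reply is that the study is preliminary, states its metrics openly, and does not bar descriptive reporting of glucagon levels. That is fair, and it is why estimation is enough here. It does not justify the broad word pharmacokinetics for a result about timing.

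**Conclusion.** The concern holds for the pharmacokinetic conclusion and for the only powered test. With unchanged rates, linear kinetics and a baseline-corrected curve, a formulation that has lost half its bioavailability would pass the t_max test about 91% of the time, exactly as often as one that has lost none. AOC_GIR might reveal the loss, but nothing in the plan says what AOC_GIR result would count against Xeris, and the unequal doses in Section V.d could mask it.

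The documents contain no evidence that Xeris glucagon is less bioavailable. The swine study found no difference in glucose rise at 10 mcg of each product, which is limited reassurance. The defect is that the plan names no measure that would answer the question in humans. The t_max test remains valid for what it tests, so this should be corrected but does not undermine the design.

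**What to change.** - **Section VI.b:** add baseline-subtracted plasma glucagon AUC0-60 and Cmax as secondary endpoints. For each, take the within-subject difference of logs (Xeris minus Lilly), exponentiate the mean, and report the geometric mean ratio with its confidence interval as an estimate. Define the baseline for each injection; Section V.d plans two baseline samples before the first injection but names none for the second, where routine plasma sampling can supply it.
- **Scaling:** report each ratio both raw and per mcg injected. If the doses differ, state that the second assumes dose proportionality, which the documents do not establish.
- **Section II:** limit any conclusion from t_max and t½max alone to rate of absorption.
- **Doses:** reconcile Sections V.d, V.e and VII before any exposure ratio or AOC_GIR is interpreted.

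The cost is a few lines of text and the dose reconciliation, with no new samples, assays or subjects. The intervals may be wide with 12 pairs. A powered exposure test cannot be sized from these documents, which give neither an exposure SD nor an exposure margin.

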- The subject will remove their own insulin pump and a primed continuous insulin infusion will be started using the insulin/saline/albumin mixture. The continuous rate will be between two-fold and four-fold higher than the mean basal insulin rate of the subject. The insulin infusion may be used to give insulin boluses if the subject is hyperglycemic at arrival to reduce the time necessary to reach steady state. Once the appropriate rate is established (with a dextrose infusion rate that is neither too low nor too high), it will remain stable throughout the experiment. For a 70 kg, 5'10" tall man with a usual basal rate of 1 u/hr, an infusion at two-fold the usual basal rate would be 17 mU/m²/min. Therefore, for a 5 ml/hr infusion 19.88 units of insulin would be added to 50 ml of saline/albumin solution (~0.4 u/ml).
- An infusion of 20% dextrose in water will be started. BG values will be measured every five minutes using arterialized blood measured with the HemoCue. The dextrose infusion will be adjusted so that the blood glucose is stabilized at 90 ± 5 mg/dl. This is expected to take approximately two hours. If the dextrose infusion rate is less than 2 mg/kg/min or greater than 8 mg/kg/min then the insulin infusion rate may be adjusted. For the 70 kg, 5'10" tall man this would correspond to 42-168 ml/hr. If this process takes longer than 3 hours, the study will be stopped.
- Blood samples (2 ml) will be processed for plasma for later insulin and glucagon measurement every 20 minutes throughout the experiment.

- Once the insulin infusion rate is established and the dextrose infusion rate has been stable for 20-30 minutes with the BG in the target range, two baseline plasma samples will be obtained and the first glucagon injection will be given.
- The order of glucagon injections will be randomized and double blinded. Neither the subject nor the provider running the experiment will know what each injection is. The study nurse will prepare the medications and label the syringes "1" and "2", for the order of injection.
- An injection of 30 mcg of Lilly glucagon or 50 mcg of Xeris glucagon (the order will be determined by block randomization) will be administered by subcutaneous injection using a syringe and a small gauge needle at a depth of less than 1 cm.

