- In the 60 minute period after the glucagon injection, the frequency of BG checks will be increased to every two minutes and blood samples will be processed for plasma at each check. After this 60 minute period, the sampling interval will return to 5 minutes and blood samples will be processed for plasma every five minutes until the GIR has stabilized for three samples, when the sampling interval will be reduced to every 20 minutes.
- The dextrose infusion rate will be adjusted to maintain the BG in the target range. Since glucagon antagonizes the effects of insulin in the liver, the dextrose infusion rate will be reduced and then increased again to baseline as the glucagon effect waxes and wanes.
- The injection site will be examined every five minutes for the first 15 minutes after injection and then every 15 minutes until 1 hour after the injection. Any local reactions will be documented, including a qualitative description and measurement of any skin reaction.
 - Dermal responses will be measured after each injection using the Draize scale, which quantifies erythema and eschar, and edema on a scale of 0-4, with 0 representing none and 4 representing severe.
- Subjects will be asked to rate the pain associated with injection on a 10 cm standard visual analog scale (VAS): 0 = no pain, 10 = worse imaginable pain
- Subjects will be asked at one hour after the injection to rate their maximal nausea during the preceding hour on a VAS: 0 = no nausea, 10 = vomiting
- Given what is known about the pharmacokinetics of glucagon given by the subcutaneous route, it is expected that it will take 60-90 minutes for the dextrose infusion rate to stabilize again.
- Once the dextrose infusion rate has remained stable for 20-30 minutes with the BG in the target range, the second glucagon injection will be given.
- A 30 mcg injection of Lilly glucagon or 50 mcg injection of Xeris glucagon (whichever formulation was not given in the first injection) will be administered by the subcutaneous route using a syringe and a small gauge needle at a depth of less than 1 cm.

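### Every subject gets 30 mcg Lilly and 50 mcg Xeris, so the AOC_GIR and nausea comparisons mix formulation with a 1.67-fold dose difference and cannot support section II's AUC_GIR non-inferiority hypothesis

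*Combined protocol and SAP*

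**What the plan says.** **Doses.** For the first injection, V.d specifies "An injection of 30 mcg of Lilly glucagon or 50 mcg of Xeris glucagon". For the second, it specifies "A 30 mcg injection of Lilly glucagon or 50 mcg injection of Xeris glucagon (whichever formulation was not given in the first injection". Block randomisation decides the order only. VI.c confirms that each clamp contains one injection of each product.

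**Other dose statements.** I.d describes "micro-doses (0.05 and 0.03 mg) of freshly reconstituted Lilly glucagon with Xeris glucagon" without tying either dose to a product. V.e gives a total of 80 mcg per subject. VII gives 100 mcg.

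**Hypothesis.** Section II expects Xeris to be non-inferior on pharmacokinetics, "and pharmacodynamics (AUC_{GIR}), and in terms of safety".

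**Endpoints and analysis.** In VI.b the primary endpoint, t_max, is the only one marked "for Xeris vs. Lilly (non-inferiority". The pharmacodynamic secondary endpoint is "Area over the curve for glucose infusion rate in the hour following a subcutaneous glucagon dose", compared between products. Maximal nausea in the hour after injection is also compared between products. For the analysis, "We will use paired t-test for comparison of means", with regression models that adjust for demographics. The only glucagon-level endpoints are times (t_max and t_1/2max), although V.d has plasma processed every two minutes for an hour after each injection.

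**Purpose.** I.d says the head-to-head comparison will provide "preliminary data required to obtain FDA evaluation of Xeris glucagon in future bionic pancreas studies".

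**The concern.** A crossover removes differences between subjects. It cannot remove a difference that travels with the product in every subject. Here dose travels with formulation, so randomising the order, pairing and demographic adjustment all leave the two inseparable.

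The direction matters. V.d explains that glucagon lowers the dextrose requirement, so a stronger effect means a larger AOC_GIR. With an increasing dose-response, the higher Xeris dose pushes AOC_GIR towards the conclusion that section II hopes for. An equal or larger AOC_GIR for Xeris would not show that the formulation matches Lilly at the same dose. A smaller one would still count against Xeris. For nausea, which V.e recognises as a possible glucagon effect, the imbalance works the other way and could make Xeris look less tolerable than it is.

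At stake is how these results are read when they are used to support further bionic pancreas work. The visible text gives no reason for the split; one could lie in the appendices or other pages that were not available for review.

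**Working it through.** **1. The plan's own figure (VI.c).** Inputs: SD 3.52 min per product, correlation 0.7, margin 2.52 min, true difference 0, one-sided alpha 0.05.
- SD of the paired difference = 3.52 × √(2 × (1 − 0.7)) = 2.727, stated as 2.73.
- Noncentrality at n = 12 is (2.52 / 2.73) × √12 = 3.20 on 11 df, giving power 0.911. At n = 11 the same formula gives 0.885.
- The smallest n with 90% power is therefore 12, as stated.

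**2. Doses and totals.**

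| Lilly / Xeris (mcg) | Dose ratio | Total (mcg) | Agrees with |
|---|---|---|---|
| 30 / 50 | 1.67 | 80 | V.d, V.e |
| 50 / 50 | 1.00 | 100 | VII |
| 30 / 30 | 1.00 | 60 | none |

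Only the two V.d injection steps say which product gets 50 mcg. The 80 mcg in V.e fits either assignment. I.d names both doses but assigns neither.

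**3. Break-even potency.** Let the response be an increasing function f of (potency × dose), with Lilly's potency set to 1 and Xeris's to r. The trial compares f(50r) with f(30). These are equal when 50r = 30, so r = 0.60. This holds for any increasing f; no slope is needed.

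**4. Size, as illustration only.** Assume AOC_GIR is proportional to dose^b. The documents do not give b. With identical potency, the expected Xeris/Lilly ratio is (50/30)^b:

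| b | 0.25 | 0.5 | 0.75 | 1 |
|---|---|---|---|---|
| Ratio | 1.14 | 1.29 | 1.47 | 1.67 |

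Assume further a ratio margin of 0.80, n = 12, one-sided 0.05, a log-scale paired analysis, and a within-subject ratio CV of 20% to 50%. Take a product whose true equal-dose ratio sits exactly at 0.80. At 30/50 its log-ratio is shifted by b × ln(50/30), so noncentrality = b × ln(50/30) × √12 / √(ln(1 + CV²)). The chance of wrongly declaring non-inferiority, nominally 5%, becomes:

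| b | CV 50% | CV 30% | CV 20% |
|---|---|---|---|
| 0.25 | 22% | 41% | 67% |
| 0.5 | 54% | 88% | 99% |
| 1 | 97% | >99.9% | >99.9% |

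The margin, CV, slope and log scale are all assumptions. VI.b plans a paired t-test of means and does not mention logs.

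**5. Volumes (V.b: Xeris 5 mg/ml, Lilly 1 mg/ml).** Xeris 50 mcg is 50/5 = 10 microlitres, and 30 mcg is 6. Lilly 30 mcg is 30 microlitres, and 50 mcg is 50.

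**6. Exposure check from planned samples.** For an assumed paired log-SD of 0.3 to 0.5, the 95% CI for dose-normalised relative exposure is the estimate times or divided by exp(2.201 × SD / √12), which is 1.21 to 1.37. That is feasible but imprecise.

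**The case against.** The best defence is that no specified test is broken. AOC_GIR is secondary, carries no margin and is not marked as non-inferiority in VI.b. Section II states a hypothesis, does not speak of potency per mcg, and the study is preliminary. This stands as a limit on scope. It does not rescue the hypothesis, which is worded as one formulation against another while the design compares 50 mcg of one with 30 mcg of the other.

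Several further points also stand:
- The absence of a dose term is not itself the fault. With one dose per product, such a term could never be estimated.
- Equal doses alone would not create a non-inferiority test; a margin is needed. Power would also be modest. Suppose Xeris has 80% of Lilly's potency at equal doses, with n = 12, a two-sided 0.05 paired test on the log scale and a paired log-SD of 0.3 to 0.5. The chance of finding Xeris significantly lower is then 29% to 65% if b = 1, and 11% to 22% if b = 0.5.
- Equalising at 30 mcg would cut an already very small Xeris volume to 6 microlitres, which could worsen dosing accuracy.

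A reader might infer that the t_max test or N = 12 is undermined. The dose imbalance does apply to those injections, but the documents do not show that t_max depends on dose, and the sample size reproduces. A reader might also infer that the split was chosen to favour Xeris. Nothing in the documents says so, and VII's total leaves open that 50/50 was intended.

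**Conclusion.** The point holds for the secondary AOC_GIR and nausea comparisons. That formulation and dose are inseparable follows directly from V.d and needs no assumption. The direction of the bias assumes an increasing dose-response, and the 60% break-even also assumes that potency acts as a scaling of dose. On that basis, the AUC_GIR non-inferiority hypothesis in section II cannot be supported as a statement about formulation.

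The actual size of the bias is unknown, since the documents supply no dose-response, SD or margin for AOC_GIR. The modelled percentages show what could happen; they do not estimate what will happen, and they should not be quoted as the trial's error rate. The primary analysis is not challenged. This should be fixed before dosing, but it does not invalidate the study.

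**What to change.** **First**, before the first clamp, have the sponsor confirm the intended doses and reconcile V.d, V.e and VII.

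**Preferred: 50 mcg of each.** This matches the total in VII, keeps the Xeris volume at 10 microlitres, and uses the Lilly dose from which VI.c took its t_max figures. Update V.d and V.e. Report the AOC_GIR difference or ratio with a 95% CI, and claim non-inferiority only if a margin is prespecified. The cost is a protocol amendment under the investigator-held IND, with IRB and DSMB involvement, and a Lilly dose raised by 50/30 − 1 = 67%.

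**If 30/50 is kept:**
- state the reason in V.d;
- remove AUC_GIR non-inferiority from section II;
- label the AOC_GIR and nausea results as 50 mcg Xeris vs 30 mcg Lilly, with 95% CIs and no per-mcg claim;
- optionally prespecify dose-normalised plasma glucagon AUC, from samples already planned, as supportive;
- correct the total in VII to 80 mcg.

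This route needs wording changes only, at the price of a narrower pharmacodynamic conclusion. Neither route changes N = 12 or the primary test.

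### The secondary endpoint GIR_max takes a maximum of a rate that glucagon is expected to lower, so it mainly returns the pre-dose or recovered rate and not the size of the effect

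*Combined protocol and SAP*

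**What the plan says.** Section VI.b (Study Endpoints) names two GIR-based secondary endpoints. One is the area over the GIR curve in the hour after a dose (AOC_GIR). The other is "Maximal glucose infusion rate" (GIR_max). Neither has a stated baseline, and GIR_max has no window either.

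The rest of the plan gives the direction and course of the response:

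- Section I.d, on the chosen doses: "They are expected to result in a modest but easily measureable decrease in the glucose infusion rate (GIR").
- Section V.d, after the first injection: "the dextrose infusion rate will be reduced and then increased again to baseline as the glucagon effect waxes and wanes". The same course is described after the second.
- Section V.d, on timing: "it is expected that it will take 60-90 minutes for the dextrose infusion rate to stabilize again".
- Section V.d, on optimising the procedure: GIR should drop by 20% or more after an injection, without reaching zero.
- Section V.d, before the first injection: the insulin rate is established and "the dextrose infusion rate has been stable for 20-30 minutes with the BG in the target range". An equivalent stable period precedes the second injection.

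No section defines GIR_max as a reduction, and no section lists a minimum GIR as an endpoint. Section II calls the pharmacodynamic measure AUC_GIR, whereas Section VI.b uses AOC_GIR.

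**The concern.** If a curve starts on a plateau, falls and climbs back to the plateau, its highest point is the plateau. In this clamp the plateau is set mainly by the chosen insulin infusion rate and the subject's insulin sensitivity. The glucagon formulation has little to do with it. The recovery plateau after injection 1 is also the pre-dose plateau for injection 2, so without a window one stretch of data could supply GIR_max for both formulations.

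Section II hypothesises pharmacodynamic non-inferiority, and Section I.d intends the comparison to support FDA evaluation of Xeris glucagon in later studies. A GIR endpoint that tends to agree between formulations whatever their effects could be misread as support for similarity. Depth of suppression, which the plan itself uses to judge whether an experiment is working, is not reported by any listed endpoint. AOC_GIR combines depth with duration.

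**Working it through.** **The plan's own figure.** No design figure is given for GIR_max. The only one is the sample size for t_max in Section VI.c, and it reproduces. SD of the paired difference = √(2 × 3.52² × (1 − 0.7)) = 2.73. With margin 2.52 min, true difference 0 and one-sided alpha 0.05, the paired t-test has power 88.5% at n = 11 and 91.1% at n = 12. Nothing in that calculation depends on GIR_max.

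**Inputs from the plan.** Baseline GIR of 2 to 8 mg/kg/min comes from Section V.d ("If the dextrose infusion rate is less than 2 mg/kg/min or greater than 8 mg/kg/min then the insulin infusion rate may be adjusted"). Re-stabilisation at 60 to 90 min comes from the same section.

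**Assumptions.** The documents give no curve shape, nadir time or GIR-recording interval. Assume GIR(t) = B × (1 − d × s(t)), where B is the baseline and d the fractional fall. Here s rises linearly from 0 at injection to 1 at the nadir time tp, then returns linearly to 0 at recovery time T. There is no noise; tp is 20 to 45 min and T is 60 to 90 min.

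**Step 1: window that includes the injection or runs to recovery.** There s = 0 at some point, so the maximum equals B for every d. The minimum is B × (1 − d).

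| B (mg/kg/min) | Maximum, any fall | Minimum at falls of 20% / 50% / 80% |
|---|---|---|
| 2 | 2.0 | 1.6 / 1.0 / 0.4 |
| 5 | 5.0 | 4.0 / 2.5 / 1.0 |
| 8 | 8.0 | 6.4 / 4.0 / 1.6 |

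**Step 2: readings more favourable to the endpoint.** Let the window run from a first reading at f minutes to 60 min. For two falls d1 < d2, the difference in maximal decrease is B × (d2 − d1). The difference in GIR_max is that amount times the smallest s in the window. The share of the true difference that GIR_max carries is therefore

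min( f/tp , max(0, (T − 60)/(T − tp)) ).

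- f = 0: 0% for every tp and T.
- f = 2: 0% if T = 60. At T = 75 or 90 it is 10.0%, 6.7%, 5.0% and 4.4% for tp = 20, 30, 40 and 45.
- f = 5: 0% if T = 60. At T = 75 or 90 it is 25.0%, 16.7%, 12.5% and 11.1% for the same tp.
- Window extended to 90 min: 0% in all cases.

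**Step 3: one worked case.** Take B = 5, tp = 30, T = 75.

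| Quantity | Fall 20% | Fall 50% | Fall 80% | 80% vs 20% |
|---|---|---|---|---|
| GIR_max, 0–60 min | 5.00 | 5.00 | 5.00 | 0 |
| GIR_max, 2–60 min | 4.93 | 4.83 | 4.73 | 0.20 |
| GIR_max, 5–60 min | 4.83 | 4.58 | 4.33 | 0.50 |
| Maximal decrease | 1.0 | 2.5 | 4.0 | 3.0 |

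On the same curve, the area over 0–60 min is B × d × (15 + 20) = 35, 87.5 and 140 mg/kg. The 15 is the area under s up to 30 min, and the 20 is (45² − 15²)/(2 × 45) from 30 to 60 min. AOC_GIR tracks the effect; GIR_max hardly does.

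**Step 4: a different shape.** With a sinusoidal fall to a nadir at 25 min, B = 5, recovery at 90 min and the injection time left out, GIR_max over the hour is 4.87, 4.69 and 4.50 for the three falls. The 80% versus 20% contrast is 0.37 out of 3.0, about 12%. With recovery at 60 min all three values are 5.0. The exact share depends on the shape; the pattern does not.

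**The case against.** The strongest reply is that GIR_max is probably a slip for the maximal decrease, and that little depends on it. It is one of several secondary endpoints with no margin, power statement or success criterion. AOC_GIR covers the effect, and a decrease can be computed from the recorded rates at any time. All of this is fair and limits the consequence. It does not remove the point: the words are spelled out in full, nothing in the plan redefines them, and an analyst who followed them would compute a maximum.

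A second reply is that the percentages come from an assumed noise-free curve, and that manual titration can overshoot, so a real maximum need not equal the baseline. That also stands as a limit on the figures. Overshoot or titration noise would move GIR_max, but neither measures suppression. The contrast of 20% with 80% is deliberately wide; the share carried does not depend on it.

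Third, the 20% criterion in Section V.d guides the choice of insulin rate in early experiments and is not an endpoint. Agreed; it is used here only to confirm direction. The AUC/AOC discrepancy is one of naming.

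**Conclusion.** The concern holds. As written, GIR_max does not measure how far each formulation suppresses GIR. On the triangular curve it carries 0% of a true difference in suppression if the window includes the injection or extends to recovery. It carries 0–10% for 2–60 min and 0–25% for 5–60 min. These figures describe size under assumed curves; they are not statements about power. The correction should be made, but its reach is one secondary endpoint.

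A separate limit applies to every GIR comparison, including a corrected one. Section V.d specifies "An injection of 30 mcg of Lilly glucagon or 50 mcg of Xeris glucagon", with the other formulation given second. Those amounts sum to 30 + 50 = 80 mcg, the total stated in Section V.e, but Section VII states a total of 100 mcg. These statements contradict each other and must be reconciled. If the amounts do differ between formulations, dose and formulation remain confounded in the GIR comparison even once the text agrees.

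**What to change.** In Section VI.b, replace GIR_max with the maximal decrease in GIR, absolute and percent, within the hour after injection. Measure it from the mean GIR over the 20–30 minute stable period before that same injection. State the same baseline for AOC_GIR, and use the name AOC_GIR in Section II. Reconcile the dose statements in Sections V.d, V.e and VII before any GIR difference or similarity is attributed to formulation.

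The cost of the endpoint change is wording only. Glucose infusion rates are already recorded (Section VI.a), the stable pre-dose periods are already required, and no sampling is added. The drawback is that a nadir is a single extreme value and somewhat sensitive to noise in the infusion-rate record.
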